5.5.2 Maximum Dose/Exposure for This Trial

The maximum dose in this trial will not exceed EBR 50 mg and GZR 100 mg.

6. Study Population

Male/Female participants with chronic hepatitis C GT1 or GT4 virus infection from the age of 3 years up to <18 years will be enrolled in this trial.

Prospective approval of protocol deviations to recruitment and enrollment criteria, also known as protocol waivers or exemptions, is not permitted.

6.1 Inclusion Criteria

Participants are eligible to be included in the study only if all of the following criteria apply:

Type of Participant and Disease Characteristics

1. The participant has HCV RNA ($\geq 1,000$ IU/mL in peripheral blood) at the time of screening.
2. The participant has documented chronic HCV GT1 or GT4 infection as follows:
 - a) positive for anti-HCV antibody, HCV RNA, or HCV GT1 or GT4 at least 6 months before Day 1; or
 - b) positive for anti-HCV antibody or HCV RNA with a liver biopsy consistent with chronic HCV infection (such as the presence of fibrosis) before Day 1.
3. For participants with GT4, HCV RNA $<800,000$ IU/mL at the time of screening.
4. For participants with GT1a, no evidence of NS5A RASs detected at screening at positions 28, 30, 31, and/or 93.
5. The participant has liver disease staging assessment as follows:
 - a) Absence of cirrhosis (F0 to F3) defined as any one of the following:
 - i. Liver biopsy performed within 24 months of Day 1 showing absence of cirrhosis, or
 - ii. FibroScan® performed within 12 months of Day 1 with a result ≤ 12.5 kPa (only for participants aged 12 years up to 18 years), or
 - iii. In the absence of criterion i. or ii. above, absence of cirrhosis can be determined by the investigator according to local clinical standards that includes physical examination during screening in combination with laboratory evaluation during screening and/or imaging test within 6 months of screening.
 - b) Compensated Cirrhosis (F4) defined as any one of the following:
 - i. Liver biopsy performed prior to Day 1 showing cirrhosis, or
 - ii. FibroScan® performed within 12 months of Day 1 with a result > 12.5 kPa (only for participants aged 12 years up to 18 years), or

- iii. In the absence of criterion i. or ii. above, cirrhosis can be determined by the investigator according to local clinical standards that includes physical examination during screening in combination with historical or current laboratory evaluation and/or imaging with findings consistent with cirrhosis (such as firm or enlarged liver, splenomegaly).

NOTE: Enrollment in the Mini Age Cohorts will be limited to non-cirrhotic participants.

6. The participant has an HCV treatment status that is one of the following:
 - a) GT1 and GT4: HCV TN (defined as no prior exposure to any interferon [IFN]-containing regimen, RBV, or other HCV-specific DAA agent).
 - b) GT1 only: HCV TE (defined as prior virologic failure during or after treatment with an IFN or pegylated-IFN with or without RBV; or intolerance to IFN or pegylated-IFN with or without RBV). Participants cannot have previously received treatment with HCV specific DAA agents (**NOTE:** GT4-infected participants cannot be HCV TE).

Demographics

7. The participant is male or female between 3 years to less than 18 years of age on day of signing informed consent/assent.
8. For participants in the Mini Age Cohorts only (these restrictions do not apply for the Expanded Age Cohorts):
 - a) Weight:
 - i. Age Cohort 1: ≥ 32 kg
 - ii. Age Cohort 2: ≥ 19 kg
 - iii. Age Cohort 3: ≥ 12 kg
 - b) Race: Participants of non-Asian Race.

Female participants:

9. A female participant is eligible to participate if she is not pregnant (see Appendix 5), not breastfeeding, and at least one of the following conditions applies:
 - a.) Not a woman of childbearing potential (WOCBP) as defined in Appendix 5
OR
 - b.) A WOCBP who agrees to follow the contraceptive guidance in Appendix 5 during the treatment period and for at least 14 days after the last dose of study treatment.

Informed Consent/Accent

10. The participant's legally acceptable representative(s) provides written informed consent for the study and, when applicable, the participant provides written informed assent.

NOTE: The participant's legally acceptable representative(s) may also provide consent for Future Biomedical Research (FBR); however, the participant may participate in the main study without participating in FBR.

Other Inclusion Criterion

11. The participant must be able to swallow the placebo to EBR/GZR (FDC) prior to allocation. This is applicable only to participants in Mini Age Cohort 1 and, if it is determined by PK analysis that Expanded Age Cohort 1 will also receive the adult FDC dose, to participants in Expanded Age Cohort 1.

6.2 Exclusion Criteria

Participants are excluded from the study if any of the following criteria apply:

Medical Conditions

1. The participant has evidence of decompensated liver disease manifested by the presence of or history of ascites, esophageal or gastric variceal bleeding, hepatic encephalopathy, or other signs or symptoms of advanced liver disease.
2. The participant is cirrhotic AND has a Child-Turcotte-Pugh score >6 , corresponding to a Child Class B or C.

NOTE: To calculate the Child-Turcotte-Pugh score and classification, refer to the following website: <http://www.mdcalc.com/child-pugh-score-cirrhosis-mortality/>.

NOTE: For participants with documented Gilbert's syndrome, use +1 for the bilirubin category of the Child-Pugh calculation.

3. The participant is co-infected with HIV.
4. Has evidence of past or present hepatitis B infection (either hepatitis B core antibody [anti-HBC] positive and/or hepatitis B surface antigen [HBsAg] positive) at screening.
5. The participant has a history of malignancy ≤ 5 years prior to signing informed consent or is under evaluation for other active or suspected malignancy including HCC.
6. A WOCBP is expecting to conceive or donate eggs from Day 1 through at least 14 days after the last dose of study treatment or longer if dictated by local regulations.
7. The participant has any of the following conditions:
 - a) organ transplants (including hematopoietic stem cell transplants) other than cornea and hair.
 - b) poor venous access that precludes routine peripheral blood sampling required for this study.

- c) history of gastric surgery (eg, stapling, bypass) or malabsorption disorders (eg, uncontrolled celiac sprue disease).
- d) any clinically significant cardiac abnormalities/dysfunction that may interfere with participant treatment, assessment, or compliance with the protocol, including but not limited to: unstable angina, unstable congestive heart failure, unstable arrhythmia; participants currently under evaluation for a potentially clinically significant cardiac abnormality/dysfunction are also excluded.
- e) any major medical condition, clinically significant illness (other than HCV), pre study laboratory or electrocardiogram (ECG) abnormality, or history of any illness, including failure to thrive, which, in the opinion of the investigator, might interfere with participant treatment, assessment, compliance with the protocol, or confound the results of the study or pose additional risk in administering the study drug to the participant.
- f) history of a medical/surgical condition that resulted in hospitalization within the 3 months prior to enrollment, other than for minor elective procedures.
- g) medical/surgical conditions that may result in a need for hospitalization during the study duration.

NOTE: Elective procedures will be permitted following 14 days after taking the last dose of study drug.

- h) any medical condition requiring, or likely to require, chronic systemic administration of corticosteroids, tumor necrosis factor antagonists, or other immunosuppressant drugs through FW24.
- i) life-threatening serious adverse event (SAE) during the screening period.
- j) Evidence of history of chronic hepatitis not caused by HCV, including but not limited to, drug-induced hepatitis, hemochromatosis, Wilson's disease, $\alpha 1$ antitrypsin deficiency, alcoholic liver disease, and autoimmune hepatitis (See Exclusion Criterion #4 regarding evidence of history of hepatitis B).

NOTE: Participants with history of acute non-HCV-related hepatitis, which resolved >6 months before study entry, can be enrolled.

8. A WOCBP who has a positive urine pregnancy test within 24 hours before the first dose of study treatment (see Appendix 5). If the urine test cannot be confirmed as negative, a serum pregnancy test is required. In such cases, the participant must be excluded from participation if the serum pregnancy result is positive.

Prior/Concomitant Therapy

9. The participant is taking or plans to take any of the prohibited medications listed in the protocol (see Section 7.7 – Concomitant Therapy) or is taking herbal supplements, including but not limited to St. John's Wort (Hypericum perforatum), from 2 weeks prior to Day 1 through 2 weeks after the study treatment period.

NOTE: For the Mini Age Cohorts only, the participant is taking or plans to take methadone or strong CYP3A inhibitors.

10. The participant has had previous HCV DAA treatment.

Prior/Concurrent Clinical Study Experience

11. The participant is currently participating or has participated in a study with an investigational compound within 30 days of signing informed consent/assent and is not willing to refrain from participating in another such study through 24 weeks after the study treatment period (FW24).

Diagnostic assessments

12. The participant has exclusionary laboratory values at the screening visit as listed in [Table 4](#) below.

NOTE: If any of the laboratory exclusion criteria below in [Table 4](#) are met, the site may have the abnormal value retested one time.

Table 4 Laboratory Exclusion Criteria

Laboratory Assessment	Exclusionary Values
Creatinine clearance (eGFR) ^a	<50 mL/min/1.73 m ²
Hemoglobin	<10 g/dL
Platelets	<100 × 10 ³ /μL
Serum Albumin	<3.0 g/dL
INR	>1.7 (unless participant has a stable INR on an anticoagulant regimen)
ALT	>10 × ULN
AST	>10 × ULN

ALT = alanine aminotransferase; AST = aspartate aminotransferase; eGFR = estimated glomerular filtration rate; INR = international normalized ratio; ULN = upper limit of normal

^a Creatinine clearance will be evaluated as eGFR based on the modification of diet in renal disease equation:

$$\text{eGFR (mL/min/1.73 m}^2\text{)} = 175 \times (\text{Scr, std})^{1.154} \times (\text{Age})^{-0.203} \times (0.742 \text{ if female}) \times (1.212 \text{ if black})$$

Scr, std: serum creatinine measured with a standardized assay

Other Exclusions

13. The participant has significant emotional problems or a clinically significant psychiatric disorder that may interfere with participant treatment, assessment, or compliance with the protocol.

14. The participant has clinically relevant drug or alcohol abuse within 12 months of screening that may interfere with participant treatment, assessment, or compliance with the protocol.

15. Is or has an immediate family member (eg, spouse, parent/legal guardian, sibling or child) who is investigational site or sponsor staff directly involved with this study.

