7.7 Concomitant Therapy

Medications or vaccinations specifically prohibited in the exclusion criteria are not allowed during the dosing period. If there is a clinical indication for any medication or vaccination specifically prohibited, discontinuation from trial therapy or vaccination may be required. The investigator should discuss any questions regarding this with the Sponsor Clinical Director. The final decision on any supportive therapy or vaccination rests with the investigator and/or the participant's primary physician. However, the decision to continue the participant on study treatment requires the mutual agreement of the investigator, the Sponsor and the participant or the participant's legally acceptable representative.

It is important for investigators to review each medication (prescription and non-prescription) the participant is taking before starting the study and at each study visit.

- All concomitant medications should be reviewed and data collected through 2 weeks after the study treatment period. Participants or the participant's legally acceptable representative should be asked about any new drugs/vaccines they are taking/have taken or changes to any previously reported drugs/vaccines.
 - Drugs known to be hepatotoxic (ie, drugs with a warning of hepatotoxicity in the package insert) should be avoided. Investigators are encouraged to review each medication for potential hepatotoxicity using the website www.livertox.nih.gov.
- To minimize the risk of adverse drug interactions, every effort should be made to limit the number of concomitant drugs to those that are truly essential.
- Non-study HCV medications/therapies, including IFN, are prohibited through FW24. Any use should be reported throughout the study duration.

Prohibited Medication

Specific restrictions for concomitant therapy are listed in [Table 6](#). The medications/therapies are not permitted during the dosing period and for 14 days thereafter.

Table 6 List of Prohibited Medications

Known hepatotoxic drugs	Etifoxine, isoniazid, nitrofurantoin, phenytoin, oral ketoconazole
Herbal supplements	Including, but not limited to: St. John's wort
Strong and moderate CYP3A/P-gp inducers, including but not limited to	Anti-infectives: nafcillin, rifampin Anticonvulsants: carbamazepine, phenytoin, phenobarbital Endothelin antagonists: bosentan Wakefulness-promoting agents: modafinil Herbal products: St. John's wort HIV medications: efavirenz, etravirine

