OATP inhibitors	Immunosuppressants: cyclosporine Anti-infectives: rifampin HIV medications: atazanavir, darunavir, lopinavir, saquinavir, tipranavir
HCV medications	All non-study HCV medications/therapies
HIV medications, including but not limited to	All boosted and unboosted HIV protease inhibitors including, but not limited to: atazanavir, darunavir, lopinavir, saquinavir, tipranavir Cobicistat-containing regimens: elvitegravir/cobicistat/emtricitabine/tenofovir (disoproxil fumarate or alafenamide) efavirenz etravirine
HMG-CoA reductase inhibitors (statins)	All statins are prohibited during the dosing period of the study
Investigational agents	All investigational agents (aside from study-related therapies)
Systemic corticosteroids	Systemic corticosteroid use for more than 2 weeks (except pulmonary/nasal administration)

AE=adverse event; CYP3A/P-gp=cytochrome P4503A/P-glycoprotein; HCV=hepatitis C virus; HIV=human immunodeficiency virus; HMG-CoA=3-hydroxy-3-methylglutaryl-coenzyme A; OATP=organic anion-transporting polypeptide.

In addition to the medications listed in [Table 6](#), participants in the Mini Age Cohorts are prohibited from taking the following medications:

- Strong CYP3A inhibitors: Including but not limited to, clarithromycin, telithromycin, itraconazole, ketoconazole, nefazodone
- Methadone

Allowed Medications

Table 7 List of Allowed Medications

Commonly Used for the Pediatric Population	
Hypoglycemic agents	Insulin, sitagliptin, glipizide, metformin
Contraceptives	Oral contraceptive pills, progesterone injects, intrauterine devices
Antidepressants/anxiolytics	Citalopram, paroxetine, duloxetine, escitalopram, fluoxetine, bupropion, trazodone, diazepam, clonazepam, temazepam, lorazepam
Acid reflux	Acid blockers: H ₂ blockers and proton pump inhibitors
Asthma	histamine blockers, inhaled/nasal corticosteroids, montelukast
Less Commonly Used for the Pediatric Population	
Anti-coagulants	Warfarin, heparin, low molecular weight heparin, aspirin, fondaparinux, desirudin, acenocoumarol

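### Exclusion 11 joins its conditions with 'and', so neither participation in another investigational study within 30 days nor unwillingness to refrain through FW24 excludes a child on its own

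*Combined protocol and SAP*

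**What the plan says.** Section 6.2 opens with the rule "Participants are excluded from the study if any of the following criteria apply". One criterion is enough to exclude, but that criterion must be met as it is worded.

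Criterion 11 describes a child now in an investigational-compound study, or one who "has participated in a study with an investigational compound within 30 days of signing informed consent/assent and is not willing to refrain from participating". The refusal concerns further studies of that kind up to FW24. The connective is 'and'.

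Two other places bear on investigational drugs:

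- Exclusion 9 (Section 6.2) covers a child who takes or plans to take a medication prohibited in Section 7.7, or who takes herbal supplements. It ends with the window "from 2 weeks prior to Day 1 through 2 weeks after the study treatment period".
- Table 6 (Section 7.7) lists "All investigational agents (aside from study-related therapies" among the prohibited medications. Its own period is stated just above the table: "The medications/therapies are not permitted during the dosing period and for 14 days thereafter".

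The opening of Section 6 adds that "Prospective approval of protocol deviations to recruitment and enrollment criteria, also known as protocol waivers or exemptions, is not permitted".

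**The concern.** A 30-day limit on earlier study participation and a commitment to stay out of other studies through FW24 serve different purposes. The first limits carry-over at entry; the second protects follow-up. Joined by 'and', each operates only when the other condition is also met. A family's refusal to promise something about future studies cannot sensibly be what activates a limit on past exposure, so this looks like a drafting error.

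The main thing at stake is the early PK. Each Mini Age Cohort has 7 children, and Section 5.1 restricts their entry in order to reduce PK variability. Day 1 AUC from at least 6 children in Mini Age Cohort 1 is reviewed before Mini Age Cohort 2 enrols. It may be used to refine that cohort's starting dose (Sections 5.5.1.2 and 10.6.2). Carry-over from another compound would be largest on Day 1. Attribution of early safety events is also exposed: under Section 5.4.2.3.2, three qualifying participants on a dose within an Age Cohort pause enrolment, so one misattributed event carries weight.

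**Working it through.** The plan states no figure on this point, so the check is a truth table, a day count and an illustrative decay calculation.

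**Step 1: the logic.** Let A = currently in an investigational-compound study; B = was in one within 30 days of consent/assent; C = not willing to refrain through FW24. The sentence allows two parses.

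| A | B | C | (A or B) and C | A or (B and C) | A or B or C (independent) |
|---|---|---|---|---|---|
| no | no | no | not excluded | not excluded | not excluded |
| no | no | yes | not excluded | not excluded | excluded |
| no | yes | no | not excluded | not excluded | excluded |
| no | yes | yes | excluded | excluded | excluded |
| yes | no | no | not excluded | excluded | excluded |
| yes | no | yes | excluded | excluded | excluded |
| yes | yes | no | not excluded | excluded | excluded |
| yes | yes | yes | excluded | excluded | excluded |

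The first parse excludes 3 of the 8 combinations, the second 5 and independent conditions 7. Rows 2 and 3 pass under both parses: the unwilling child with no recent study, and the willing child with a study in the last 30 days. Only the rows with A = yes and C = no depend on the parse.

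**Step 2: the backstop.** Let Day 1 fall k days after consent, with k from 0 to 45 (the screening window in Section 9.11.1). The 30-day limit would reach k + 30 days before Day 1. Exclusion 9 reaches at most 14.

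- k = 0: days 15 to 30 before Day 1 are not covered.
- k = 45: days 15 to 75 before Day 1 are not covered.

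Fourteen days is the favourable reading. The 2-week window may attach only to herbal supplements, and Table 6 states no pre-treatment period. Exclusion 10 covers only earlier HCV direct-acting antivirals.

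**Step 3: how much could remain.** The documents give no half-life for an unnamed earlier compound, so the half-life h is an assumption, shown over a range. Fraction remaining after t days = 2^(−t/h). The gaps compared are 14 days (text as it stands, with exclusion 9) and 30 days (a working 30-day limit with k = 0). Week 4 adds 28 days: 14 + 28 = 42 and 30 + 28 = 58.

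| Assumed h | Day 1: 14 v 30 days | Week 4: 42 v 58 days |
|---|---|---|
| 2 days | 2^(−7) = 0.8% v 2^(−15) < 0.01% | both < 0.01% |
| 5 days | 2^(−2.8) = 14% v 2^(−6) = 1.6% | 2^(−8.4) = 0.3% v 2^(−11.6) = 0.03% |
| 10 days | 2^(−1.4) = 38% v 2^(−3) = 12.5% | 2^(−4.2) = 5% v 2^(−5.8) = 2% |

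The primary PK endpoints are taken at Week 4 (Sections 4 and 10.4.1.1), where the difference is small over this range.

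**The case against.** The case on the other side is strong on consequence and weak on wording.

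- **Current participants.** A reader might infer that any child now in another drug study can enter. The text does not establish that: under the second parse every current participant is excluded. Not being excluded by criterion 11 is also not the same as being eligible, since exclusions 9 and 10 still apply. This stands.
- **Concurrent exposure.** A reader might infer that the defect permits another investigational drug during treatment. Table 6 forbids it during dosing and for 14 days afterwards, which is the window of the primary safety analysis (Section 10.6.4). After that, non-study HCV therapies remain prohibited through FW24 (Section 7.7), which protects SVR₁₂ from outside HCV treatment. This stands.
- **Size.** The 38% figure needs an assumed 10-day half-life and describes Day 1, not the primary PK time point. Being in a study is also not the same as taking a drug: a child may be in off-drug follow-up. This stands.
- **Waivers.** A reader might infer that the ban on waivers obliges sites to apply the lenient reading. It stops sites admitting children who fail a criterion; it does not compel enrolment of a child who passes. Many sites may guess the intent. That is an argument for stating it, because different guesses make eligibility differ between sites.
- **Recording.** Section 9.1.5.1 has prior medication recorded for 30 days before starting the trial, so some recent exposure would be visible to the PK analysts. Recording does not prevent entry, however, and the uncovered span can reach 75 days before Day 1.

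None of this makes the 30-day limit or the FW24 commitment operate alone. Reading 'and' as 'or' has no support in the list: criterion 2 uses the same connective for a true conjunction (cirrhosis together with a Child-Turcotte-Pugh score above 6).

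**Conclusion.** The criterion gives the wrong result when followed as written. Under either parse, participation within 30 days of consent does not exclude a child whose family will refrain, and unwillingness to refrain through FW24 does not exclude a child with no recent participation. No other section restores the 30-day limit. At best, exposure is barred from 14 days before Day 1, leaving days 15 to 30 open (consent on Day 1) and up to days 15 to 75 (full screening window).

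The practical effect is limited. Few children are likely to be involved, no stated sample size or precision figure changes, and the exposure concern falls mainly on Day 1 PK and safety attribution. Its size rests on the assumed half-life of an unknown compound and on the 2-week window in exclusion 9 applying to all prohibited medications. The documents do not support a claim that the Week 4 primary PK or SVR₁₂ is materially compromised.

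**What to change.** Split criterion 11 into two exclusions, either of which is sufficient:

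- (a) current participation in a study with an investigational compound, or participation in one within 30 days of signing consent/assent; OR
- (b) unwillingness to refrain from taking part in another such study through FW24.

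This makes the protocol's own two limits operate and removes the ambiguity about current participants. The cost is a very small loss of otherwise eligible children and a protocol amendment with IRB/IEC approval. The change could be bundled with other wording corrections. No analysis, sample size or table in Section 10 needs to change.

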9.5.1 Physical Examinations

All physical examinations must be conducted as per institutional standard by the principal investigator or subinvestigator (physician, physician assistant, or nurse practitioner) as follows:

- A complete physical examination at screening and Day 1 to include the following assessments: general appearance, head, eyes, ears/nose/throat, neck, lymph nodes, skin, lungs, heart, abdomen, musculoskeletal, and neurologic evaluations. Breast, rectal, and genitourinary/pelvic examinations should be performed when clinically indicated.
- A focused physical examination at any other visit when clinically indicated.

Investigators should pay special attention to clinical signs related to previous serious illnesses.

Height and weight will be measured and recorded per the SoA and used by the Sponsor to calculate body mass index.

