10.1 Statistical Analysis Plan Summary

Key elements of the Statistical Analysis Plan (SAP) are summarized below; the comprehensive plan is provided in Sections 10.2 to 10.12.

Study Design Overview	A Phase IIb Study to Assess the Pharmacokinetics, Safety, and Efficacy of the Combination Regimen of Elbasvir (EBR)/Grazoprevir (GZR) in Pediatric Participants Aged 3 to Less Than 18 Years with Chronic Hepatitis C Infection
Treatment Assignment	This will be an open-label, non-randomized trial. Participants infected with HCV GT1a without baseline NS5A RASs at position 28, 30, 31, and/or 93; GT1b/1-other; or GT4 with HCV RNA <800,000 IU/mL; TN or PR TE (GT1 only); cirrhotic or NC, will be treated with EBR/GZR for 12 weeks within Age Cohorts (12 to <18 years, 7 to <12 years, and 3 to <7 years). Approximately 22 participants in the oldest cohort (12 to <18 years) will be enrolled. Approximately 34 participants will be enrolled in the two younger cohorts, with 12 to 22 participants in each. The total number of participants enrolled in the three cohorts will be ~56.
Analysis Populations	PK: Per-Protocol (PP) Safety: All Participants as Treated (APaT) Efficacy: Full Analysis Set (FAS) and modified FAS (mFAS)
Primary Endpoints	AUC ₀₋₂₄ , C _{max} , C _{trough} , and CL/F of EBR and GZR.
Secondary Endpoints	1. Number of participants experiencing AEs and discontinuing study drug due to AEs. 2. SVR ₁₂ (Sustained Virologic Response 12 weeks after the end of all study therapy), defined as HCV RNA <LLOQ (either TD[u] or TND) 12 weeks after the end of all study therapy.
Statistical Methods for Key Pharmacokinetic and Efficacy Analyses	Geometric means and 95% confidence intervals (CIs) will be provided for AUC ₀₋₂₄ , C _{max} , and CL/F of EBR and GZR by age cohort and dose level. The proportion of participants achieving SVR ₁₂ will be estimated using a 95% CI (via the Clopper-Pearson method). The missing data approach will be Missing=Failure (M=F).
Statistical Methods for Key Safety Analyses	Safety and tolerability will be assessed by clinical review of all relevant parameters including AEs and laboratory tests. Descriptive statistics will be provided for these safety parameters.
Interim Analyses	Periodic safety analyses will be conducted for the accruing data and will be reviewed by an eDMC at regular intervals as outlined in the eDMC charter. This will supplement routine in house medical monitoring.

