12.2 Appendix 2: Clinical Laboratory Tests

- Laboratory tests to be performed in this study are specified in [Table 15](#) and will be conducted by the central laboratory. The total amount of blood/tissue to be drawn/collected over the course of the study (from pre-study to post-study visits), including approximate blood/tissue volumes drawn/collected by visit and by sample type per participant can be found in [Table 16](#).

Table 15 Protocol-Required Safety Laboratory Assessments

Hematology	Chemistry	Urinalysis	Other
Hematocrit	Albumin	Blood	Coagulation Panel –PT –INR
Hemoglobin	ALP	Glucose	Choriogonadotropin beta (urine pregnancy test kits to sites)
Platelet count	ALT	Protein	Serum human chorionic gonadotropin (reflex when urine pregnancy test is “positive”)
RBC	AST	Specific gravity	HCV, Genotype
WBC	Bicarbonate	Microscopic exam (if abnormal results are noted)	HCV, Viral Load RNA (quantitative)
WBC Differential (result in % and Abs) –Basophils –Eosinophils –Lymphocytes –Monocytes –Neutrophils (Total)	Calcium	Bilirubin	FibroScan®
	Chloride	Ketones	
	Creatinine	Leukocyte esterase	Hepatitis B Serology Panel –HBsAg (perform at screening in all participants) –Anti-HBc, Total (screening only)
	Creatinine clearance (eGFR estimated by MDRD–NKDEP) (screening only)	Nitrite	HIV Serology Panel –HIV, Types 1 & 2 –HIV, Types 1 & 2 Confirmation by Inno-Lia HIV score–
	CPK	pH	(

Hematology	Chemistry	Urinalysis	Other
	GGT	WBC	
	Amylase	Bacteria	
	Lipase	Squamous epithelial cells	
	Glucose	RBC	
	Phosphorus		
	Potassium		
	Sodium		
	Total bilirubin		
	Direct bilirubin (if total bilirubin is elevated above the ULN)		
	Total protein		
	Blood urea nitrogen		

ALP=alkaline phosphatase; ALT=alanine aminotransferase; Anti-HBc=hepatitis B core antibody; Anti-HBs=hepatitis B surface antibody; AST=aspartate aminotransferase; CPK=creatine phosphokinase; eGFR=estimated glomerular filtration rate; GGT=gamma-glutamyl transpeptidase; HBsAg=hepatitis B surface antigen; HCV=hepatitis C virus; HIV=human immunodeficiency virus; INR=international normalized ratio; MDRD-NKDEP=Modification of Diet in Renal Disease–National Kidney Disease Education Program; PT=prothrombin time; RBC=red blood cell; RNA=ribonucleic acid; ULN=upper limit of normal; WBC=white blood cell.

Abbreviated blood chemistry includes only ALT, AST, ALP, total bilirubin, albumin, GGT, and CPK

Table 16 Approximate Blood Volumes Collected

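### The <50 renal exclusion is computed by MDRD, which has no body-size term, from age 3, so the limit has little effect at about 3 to 5 years and acts below its stated level in older children, by less as age rises

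*Combined protocol and SAP*

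**What the plan says.** Section 6.2, Table 4 sets one numeric renal limit for eligibility, an eGFR of "<50 mL/min/1.73 m"². Footnote a gives the method: "Creatinine clearance will be evaluated as eGFR based on the modification of diet in renal disease equation". The printed formula uses standardized serum creatinine, age, a factor of 0.742 for females and a factor of 1.212 for black participants. It contains no height, weight or surface-area input. Appendix 2, Table 15 names the same method: "eGFR estimated by MDRD–NKDEP", at screening only.

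The rule has no variant by age. Inclusion criterion 7 in Section 6.1 reads: "The participant is male or female between 3 years to less than 18 years of age on day of signing informed consent/assent". Section 10.1 plans about 34 of the roughly 56 participants in the two younger cohorts. For the rest it says: "Approximately 22 participants in the oldest cohort (12 to <18 years) will be enrolled".

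Height is available. Section 9.5.1 says: "Height and weight will be measured and recorded per the SoA". The Schedule of Activities includes it at screening. The only use that Section 9.5.1 gives for it is body mass index.

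**The concern.** Creatinine production follows muscle mass. A small child makes less creatinine than an adolescent, so the creatinine that corresponds to a given GFR per 1.73 m² should be lower in the small child. The equation moves the other way: its age term grows as age falls, and nothing in it offsets this for body size. A fixed cut-off of 50 on this scale therefore stands for a more severe renal impairment in a small child than in an adolescent.

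At stake is whether the criterion does what it states. A young child whom it is meant to exclude could pass screening with an apparently normal eGFR, be dosed, and enter the PK and safety summaries.

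**Working it through.** **Inputs from the documents.** Coefficient 175, age exponent -0.203, female factor 0.742, cut-off 50 (Table 4 and footnote a). The documents give no worked eGFR, so there is no stated figure to reproduce.

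**Inputs that are assumptions.** Creatinine is in mg/dL. The creatinine exponent is read as -1.154; the available text shows it without a minus sign, which may be an effect of reading the PDF. All examples are participants for whom the 1.212 factor does not apply. That factor would raise the estimate further.

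**Step 1: from the equation alone.** Let A = 175 × age^-0.203 (× 0.742 for girls). Then eGFR = A × Scr^-1.154, and the creatinine at eGFR 50 is (A/50)^(1/1.154).

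| Age | A, boys | Scr at cut-off, boys | Scr at cut-off, girls |
|---|---|---|---|
| 3 | 140.0 | 2.44 | 1.88 |
| 7 | 117.9 | 2.10 | 1.62 |
| 17 | 98.5 | 1.80 | 1.39 |

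At equal creatinine, a 3-year-old is credited with 140.0/98.5 = 1.42 times the GFR of a 17-year-old of the same sex. At 1.0 mg/dL, a 3-year-old reads 140 (boy) or 104 (girl). This step needs no creatinine-to-height relation.

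**Step 2: size of the error, under a stated assumption.** The documents give no relation between creatinine and GFR in children. Assume GFR = k × height (cm)/Scr, with k = 0.413 and a range of 0.35 to 0.55, and typical heights as shown. The creatinine at a GFR of 50 is k × height/50, which is then put through the protocol's equation. The GFR at which exclusion starts to act is k × height divided by the cut-off creatinine.

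Worked case, boy of 4 years and 100 cm:
- Scr at a GFR of 50: 0.413 × 100/50 = 0.826 mg/dL.
- Protocol eGFR: 132.1 × 0.826^-1.154 = 165.
- Cut-off creatinine: (132.1/50)^(1/1.154) = 2.32 mg/dL.
- GFR at which exclusion acts: 0.413 × 100/2.32 = 17.8.

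For a girl of the same age and height, the reading is 0.742 × 165 = 122.

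| Participant | GFR of 50 reads as (k range) | Exclusion acts below a GFR of (k range) |
|---|---|---|
| Boy, 4 y, 100 cm | 165 (118–199) | 18 (15–24) |
| Girl, 4 y, 100 cm | 122 (88–148) | 23 (20–31) |
| Boy, 7 y, 120 cm | 119 (86–144) | 24 (20–31) |
| Girl, 7 y, 120 cm | 88 (63–107) | 31 (26–41) |
| Girl, 11 y, 144 cm | 65 (47–79) | 40 (34–53) |
| Boy, 17 y, 175 cm | 64 (46–78) | 40 (34–54) |
| Girl, 17 y, 163 cm | 52 (37–63) | 48 (41–65) |

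At 4 and 7 years, exclusion acts below 50 over the whole k range in both sexes. By 11 years in girls and 17 years in both sexes, the range includes 50.

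**The case against.** Four points can fairly be made in defence of the plan.

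- **Scope.** A reader might infer that the limit fails throughout Age Cohorts 2 and 3, or that a GFR near 50 always reads well above 100 in a child. The documents do not support that. The female factor of 0.742 lowers the reading in girls, and the bias shrinks with age. A 7-year-old girl reads about 88, and an 11-year-old girl is excluded at about the same GFR as a 17-year-old boy. The stronger reading fits only about 3 to 5 years, at the central k. This point stands and sets the scope of the finding.
- **Outside relation.** The size of the error depends on a height-based relation that the documents do not contain, and that relation is itself a creatinine estimate rather than measured GFR. This stands: the readings in Step 2 are conditional. The reversal in Step 1 is not affected.
- **Another route to exclusion.** Criterion 7e in Section 6.2 lets the investigator exclude for a major condition or a pre-study laboratory abnormality, and creatinine and urea nitrogen are reported at screening. So an affected child could be enrolled, but would not necessarily be. Table 4 is the only numeric renal limit, not the only route. Still, 7e is discretionary, and an apparently normal eGFR makes its use less likely.
- **Consequence.** Section 3.2.3.1 describes minimal urinary elimination of EBR and biliary elimination of GZR. Sections 3.1, 3.2.2.1 and 3.3 cite adult experience that includes chronic kidney disease and end-stage renal disease. This stands as a reason for low severity. It does not explain why a limit that the sponsor kept should mean different things at different ages.

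**Conclusion.** The concern holds for the youngest children and weakens with age. From the equation alone, with the exponent at -1.154 and creatinine in mg/dL, the creatinine tolerated before exclusion rises as age falls, which is the wrong direction for body size. Under the assumed relation, the limit has little effect at about 3 to 5 years. At 7 years it acts well below its stated level (about 24 in boys, 31 in girls), and in late adolescence it is closest to 50 (about 40 in boys, 48 in girls).

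Severity is low. The documents give no basis for an expected number of affected children among the roughly 56, or for a material shift in the PK or safety estimates. The defect is that the stated threshold does not measure the same renal function across the enrolled age range. Restoring the minus sign on the creatinine exponent would not cure it, because every figure here already assumes that sign.

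**What to change.** In Table 4 footnote a and in Table 15, replace MDRD with a height-based pediatric creatinine equation. The sponsor and the central laboratory should choose it and state its constant and creatinine unit. Use the height already measured at screening, and leave the limit of 50 mL/min/1.73 m² unchanged.

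The cost is a wording change and a revised laboratory calculation, with no new sample or visit. Height must reach the laboratory with the screening sample. A rare child with renal impairment would become a screen failure, as the criterion intends.
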